### **Subgroup Analyses of Adverse Events**

Analyses of AEs per subgroup will be presented for the AE overview. The number and percentage of subjects experiencing AEs as well as E/100PYs will be tabulated overall.

Subgroups used for the analyses are:

- Concomitant use of corticosteroids (yes, no)
- Baseline immunosuppressant usage (yes, no)
- Baseline azathioprine usage
- Baseline cyclosporine usage
- Baseline methotrexate usage

- Baseline mycophenolate mofetil or an equivalent drug (e.g., mycophenolic acid) usage
- Baseline tacrolimus usage

An AE overview (with number and percentage of subjects experiencing treatment-emergent AEs as well as E/100PYs) will also be presented separately for

- treatment periods with/without concomitant use of corticosteroids
- treatment periods with corticosteroid dose  $> 0$  to  $\leq 15$  mg/day
- treatment periods with corticosteroid dose  $> 15$  mg/day
- treatment periods with/without concomitant use of immunosuppressant
- treatment periods
  - without concomitant use of corticosteroids and immunosuppressant
  - with concomitant use of corticosteroids only
  - with concomitant use of immunosuppressant only
  - with concomitant use of corticosteroids and immunosuppressant

## **11.2 Analysis of Laboratory Data**

Hematology variables include: hematocrit, hemoglobin, red blood cell (RBC), white blood cell (WBC), WBC differentials (neutrophils, lymphocytes, monocytes, basophils, eosinophils), and platelet count.

Clinical chemistry variables include: blood urea nitrogen (BUN), creatinine, total bilirubin, ALT (SGPT), AST (SGOT), alkaline phosphatase, sodium, potassium, calcium, inorganic phosphorus, uric acid, cholesterol, total protein, glucose, triglycerides, and albumin.

Urinalysis variables include: specific gravity, pH.

For quantitative laboratory parameters, mean changes from baseline in Study M11-327 to the minimum value, maximum value, and final value in the laboratory variables will be

summarized with the baseline mean, min/max/final mean, change from baseline mean, standard deviation, and median.

Laboratory data values will be categorized as low, normal, or high based on normal ranges of the laboratory used in this study. Shift tables from baseline in Study M11-327 to final values will be created. The shift tables cross tabulate the frequency of subjects with baseline values below/within/above the normal range versus final values below/within/above the normal range.

### **11.3                   Analysis of Potentially Clinically Significant Laboratory Values**

For selected laboratory parameters (hematology: Hemoglobin, Lymphocytes, Neutrophils, Platelet Count, WBC; clinical chemistry: Albumin, Alkaline Phosphatase, ALT, AST, Total Bilirubin, Calcium, Cholesterol, Creatinine, Glucose, Inorganic Phosphorus, Potassium, Sodium, Triglycerides) with Common Toxicity Criteria (CTC) criteria, Potentially Clinically Significant Laboratory Findings (Common Toxicity Criteria CTC Grades 3 and 4) will be assessed.

For definition of CTC V3.0 criteria, see <http://ctep.cancer.gov/reporting/ctc.html>.

The following table describes the Criteria for Potentially Clinically Significant Laboratory Findings:

Laboratory Parameter	CTC Grade 1	CTC Grade 2	CTC Grade 3	CTC Grade 4
Hemoglobin	< LLN – 100 g/L	< 100 – 80 g/L	< 80 – 65 g/L	< 65 g/L
Lymphocytes	< LLN – 0.8 × 10  /L	< 0.8 – 0.5 × 10  /L	< 0.5 – 0.2 × 10  /L	< 0.2 × 10  /L
Neutrophils	< LLN – 1.5 × 10  /L	< 1.5 – 1.0 × 10  /L	< 1.0 – 0.5 × 10  /L	< 0.5 × 10  /L
Platelet count	< LLN – 75.0 × 10  /L	< 75.0 – 50.0 × 10  /L	< 50.0 – 25.0 × 10  /L	< 25.0 × 10  /L
WBC	< LLN – 3.0 × 10  /L	< 3.0 – 2.0 × 10  /L	< 2.0 – 1.0 × 10  /L	< 1.0 × 10  /L
Albumin	< LLN – 30 g/L	< 30 g/L – 20 g/L	< 20 g/L	—
Alkaline Phosphatase	> ULN – 2.5 × ULN	> 2.5 – 5.0 × ULN	> 5.0 – 20.0 × ULN	> 20.0 × ULN
ALT	> ULN – 2.5 × ULN	> 2.5 – 5.0 × ULN	> 5.0 – 20.0 × ULN	> 20.0 × ULN
AST	> ULN – 2.5 × ULN	> 2.5 – 5.0 × ULN	> 5.0 – 20.0 × ULN	> 20.0 × ULN
Total Bilirubin	> ULN – 1.5 × ULN	> 1.5 – 3.0 × ULN	> 3.0 – 10.0 × ULN	> 10.0 × ULN
Calcium	> ULN – 2.9 mmol/L < LLN – 2.0 mmol/L	> 2.9 – 3.1 mmol/L < 2.0 – 1.75 mmol/L	> 3.1 – 3.4 mmol/L < 1.75 – 1.5 mmol/L	> 3.4 mmol/L < 1.5 mmol/L
Cholesterol	> ULN – 7.75 mmol/L	> 7.75 – 10.34 mmol/L	> 10.34 – 12.92 mmol/L	> 12.92 mmol/L
Creatinine	> ULN – 1.5 × ULN	> 1.5 – 3.0 × ULN	> 3.0 – 6.0 × ULN	> 6.0 × ULN
Glucose	> ULN – 8.9 mmol/L < LLN – 3.0 mmol/L	> 8.9 – 13.9 mmol/L < 3.0 – 2.2 mmol/L	> 13.9 – 27.8 mmol/L < 2.2 – 1.7 mmol/L	> 27.8 mmol/L < 1.7 mmol/L
Inorganic Phosphorus	< LLN – 0.8 mmol/L	< 0.8 – 0.6 mmol/L	< 0.6 – 0.3 mmol/L	< 0.3 mmol/L
Potassium	> ULN – 5.5 mmol/L < LLN – 3.0 mmol/L	> 5.5 – 6.0 mmol/L —	> 6.0 – 7.0 mmol/L < 3.0 – 2.5 mmol/L	> 7.0 mmol/L < 2.5 mmol/L
Sodium	> ULN – 150 mmol/L < LLN – 130 mmol/L	> 150 – 155 mmol/L —	> 155 – 160 mmol/L < 130 – 120 mmol/L	> 160 mmol/L < 120 mmol/L
Triglycerides	> ULN – 2.5 × ULN	> 2.5 – 5.0 × ULN	> 5.0 – 10 × ULN	> 10 × ULN

LLN = lower limit of normal range; ULN = upper limit of normal range

Shift tables from baseline value in Study M11-327 to worst value will be created. The shift tables cross tabulate the frequency of subjects with baseline values with CTC<3/CTC≥3 versus worst values with CTC<3/CTC≥3. Furthermore, for subjects with laboratory values with CTC ≥ 3, the whole course of the parameter will be listed.

## 11.4 Analysis of Liver Specific Laboratory Tests

The liver specific laboratory tests include ALT/SGPT, AST/SGOT, alkaline phosphatase and total bilirubin. Each of these laboratory values will be categorized as follows:

1.  $< 1.5 \times \text{ULN}$ ,
2.  $\geq 1.5 \times \text{ULN}$  TO  $< 3 \times \text{ULN}$ ,
3.  $\geq 3 \times \text{ULN}$  TO  $< 5 \times \text{ULN}$ ,
4.  $\geq 5 \times \text{ULN}$  TO  $< 8 \times \text{ULN}$ , and
5.  $\geq 8 \times \text{ULN}$ ,

where ULN is the upper normal limit.

For each variable, shift tables will be generated that cross tabulate the number of subjects with baseline values in Study M11-327 in these 5 categories versus the min/max/final value in these 5 categories.

A listing of potentially clinically significant liver function laboratory values will be provided. The listing will include all subjects who meet any of the following 4 criteria:

1.  $\text{ALT} \geq 2.5 \times \text{ULN}$ , or
2.  $\text{AST} \geq 2.5 \times \text{ULN}$ , or
3. Alkaline phosphatase  $\geq 2.5 \times \text{ULN}$ , or
4. Total bilirubin  $\geq 1.5 \times \text{ULN}$ .

## **11.5 Analysis of Vital Signs**

Vital signs include: Blood Pressure (Systolic/Diastolic) (mmHg), Pulse (bpm), Respiratory Rate (rpm), Temperature (°C).

Mean changes from baseline in Study M11-327 to the minimum value, maximum value, and final value in the vital signs variables will be summarized with the baseline mean, min/max/final mean, change from baseline mean, standard deviation, and median.

## **11.6 Analysis of Other Safety Variables**

Other safety variables are:

- Intraocular pressure (0–9, 10–21, 22–25, 26–30, > 30 mmHg)
- Nuclear opacity (grade < 1.0, 1.0, 1.5, 2.0, 2.5, 3.0, > 3.0)
- Cortical lens opacity (grade < 1.0, 1.0, 1.5, 2.0, 2.5, 3.0, > 3.0)
- Posterior subcapsular opacity (grade < 1.0, 1.0, 1.5, 2.0, 2.5, 3.0, > 3.0)
- 2-step increase in lens opacity (defined as change from grade < 1.0 to 2.5 or higher, from 1.0 to 3.0 or higher, or from 1.5 to > 3.0) in at least one eye in at least one of the three opacity variables

For each variable, shift tables will be generated that cross tabulate the number of subjects with baseline values in Study M11-327 in the above categories versus the worst observations (i.e., largest values) in these categories.

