3.4 Unmet Medical Need

In the US, it is estimated that about 10% of cases of blindness are due to uveitis.¹⁰ In a retrospective Dutch study, all anatomical sites of inflammation of uveitis were shown to

have the potential to lead to visual impairment and blindness; however, the risks were highest for those with panuveitis and posterior uveitis.⁴ Cystoid macular edema (CME) was identified as the leading cause of visual impairment (41%) and blindness (29%) in patients with uveitis. Therefore, there is a need to have adequate therapy in patients with all types of uveitis, particularly with posterior segment involvement given its higher risk for potential permanent disability.

The only drug class approved in the US by the Food and Drug Administration (FDA) for the treatment of uveitis is corticosteroids. An example is Retisert[®] (fluocinolone acetonide intravitreal implant), which is designed to release therapeutic levels of drug over approximately 30 months.¹¹ This is currently approved for the treatment of chronic non-infectious uveitis affecting the posterior segment of the eye. The 34-week interim results of a 3-year, prospective, randomized, dose-masked trial in subjects with unilateral or bilateral uveitis showed a significant reduction in flare rates in the implanted eye but a significant increase in flare rates in the contralateral, non-implanted eye.¹² More importantly, 3-year results showed statistically significantly higher incidence of chronic corticosteroid-associated effects in implanted versus non-implanted eyes such as need for glaucoma surgery (40% versus 2%, $P < 0.01$) and cataract extraction (93% versus 20%, $P < 0.01$).¹³

In the European Union, the only drug class widely approved for treatment of uveitis is likewise corticosteroids for systemic or local administration. In addition, the immunosuppressive agent cyclosporine holds national licenses for treatment of uveitis in some European countries. The registered indication of cyclosporine does differ between these countries and comprises the treatment of intermediate or posterior uveitis and Behcet's disease but partially restricts the usage to patients at risk of blindness, and when conventional (corticosteroid) therapy is not adequate or unjustifiable side effects occur.

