Vital signs will be obtained at each visit. This includes sitting blood pressure, heart rate, respiratory rate and body temperature. Each subject's height used in the analysis will be taken from the Screening visit of the parent study (Study M10-877 or Study M10-880). For this study, Baseline weight and vital signs measurements will be taken from the final visit of the parent study for the purposes of analysis if Study M11-327 Baseline visit occurs \leq 14 days since the last visit from the parent study (Study M10-877 or Study M10-880). If the Baseline visit occurs greater than ($>$) 14 days after the last visit from the parent study, baseline weight and vital signs measurements will be taken at that Baseline visit. Weight will be measured at the Unscheduled visit (if applicable) and Final/Early Termination visit.

Best Corrected Visual Acuity Testing

Refraction and assessment of best corrected visual acuity (BCVA) will be assessed at every visit.

At each visit, subjects should undergo refraction and the result of refraction for each eye will be recorded on the eCRF.

Using the appropriate corrective lenses based on that visit's refraction, subject's BCVA is measured using an ETDRS chart which will be specified and provided if necessary by the sponsor. Please refer to the Visual Acuity Manual provided by the sponsor for instructions.

A qualified and trained health care professional must perform the refraction and BCVA testing. Specific training and instructions will be provided by the sponsor.

Slit Lamp Exam

The slit lamp exam will be conducted at each study visit to assess the following findings: Anterior chamber cell count and Age-Related Eye Disease Study (AREDS) lens opacity grading.^{3,37,38} Slit lamp examination for AC cells is performed prior to application of mydriatic eyedrops to dilate subject's pupils for further assessment.

The AREDS classification does not apply to a subject, if he/she has pseudophakia.

The number of AC cells observed within a 1 mm × 1 mm slit beam will be recorded for each eye. The reported number will be used to determine the grade according to the SUN criteria³ (Table 2).

Table 2. Anterior Chamber Cells

Grade	Cells in Field
0	< 1
0.5 +	1 – 5
1 +	6 – 15
2 +	16 – 25
3 +	26 – 50
4 +	> 50

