Appendix F. AREDS 2008 Clinical Lens Opacity Grading Procedures

AREDS Study Group

- Dilate pupils to at least 5 mm diameter
- Use slit lamp with ~10× magnification
- Use brightest beam intensity
- Nuclear opacity
 - Orient beam at 45° to viewing axis
 - Adjust slit beam to standard parameters: 8 mm height and 0.3 mm width
 - Compare opalescence of nucleus with that in standard photos
- Cortical and PSC opacities
 - Select wide slit beam setting optimum for retro-illumination of lens
 - Visualize lens opacities against red fundus reflex background
 - Count only opacities definitely visible against red reflex
 - Mentally combine all cortical opacities into one contiguous area
 - Compare total opacity area with that in standard photos
- Classify each opacity with scale defined by 3 standard photos
- Select nearest half-step
 - Similar to standard or between two standards
 - Obviously less than mildest standard or greater than most severe

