### 5.1 Definition for Analysis Sets

Safety analyses will be conducted in the safety set. The safety set includes all subjects who received at least one dose of study medication.

Efficacy analyses will be provided for the Intent-to-Treat (ITT) set. The ITT set includes all subjects who received at least one dose of study medication. In addition, the following subjects will be excluded from the ITT set:

- Subjects who developed Exclusion Criterion No. 5 ("Subject with proliferative or severe non-proliferative diabetic retinopathy or clinically significant macular edema due to diabetic retinopathy") during the study.

- Subjects undergoing a cataract surgery during the study.
- Subjects that had previous vitrectomy or are vitrectomized during the study.
- Subjects [REDACTED] from Investigator [REDACTED] ([REDACTED] France) will be excluded because of incomplete efficacy source data in studies M10-877 and M10-880.
- Subjects from Investigator [REDACTED] ([REDACTED] USA) will be excluded because of general compliance issues in studies M10-877 and M10-880.

Both, the ITT set and the safety set will include subjects recruited in and outside Japan.

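### SAP 11.6 has no rule for on-study cataract surgery, so a lens removed before it reaches a qualifying AREDS grade counts as not having progressed

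*SAP*

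**What the plan says.** SAP Section 11.6 lists three lens variables (nuclear, cortical and posterior subcapsular), each with seven ordered categories, for example "Nuclear opacity (grade < 1.0, 1.0, 1.5, 2.0, 2.5, 3.0, > 3.0". It adds a 2-step increase, "defined as change from grade < 1.0 to 2.5 or higher, from 1.0 to 3.0 or higher, or from 1.5 to > 3.0", scored per subject "in at least one eye in at least one of the three opacity variables". For each variable, baseline is cross-tabulated "versus the worst observations (i.e., largest values) in these categories". Section 11 runs in the safety set, which is all treated subjects.

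Three other places bear on this:

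- Protocol 5.3.1.1, Slit Lamp Exam: "The AREDS classification does not apply to a subject, if he/she has pseudophakia".
- Protocol Table 3: each opacity type has a code 8.0 for a lens that cannot be graded. SAP 11.6 neither lists this code nor says how to handle it.
- SAP 5.1 removes from the ITT set "Subjects undergoing a cataract surgery during the study". On-study surgery is therefore foreseen, and those subjects remain only in the safety set.

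Section 11.6 does not mention cataract surgery, pseudophakia or a denominator.

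**The concern.** Long-term safety is the primary objective. Cataract is on the protocol's list of uveitis-related events (6.1.1.1.1) and is named in Section 3.4 as an ocular harm of corticosteroids, which this trial allows throughout. Extraction of the lens is the end stage of cataract, yet in the graded measures it simply ends the series of grades. Because SAP 5.1 also takes operated subjects out of the efficacy set, Section 11.6 is where a graded lens outcome for them should appear, and there an operated eye can look stable. No section of the SAP tabulates cataract surgery itself.

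**Working it through.** **1. Reproduce the SAP's rule.** Inputs are the seven categories in SAP 11.6 and the instruction in Protocol Appendix F, "Select nearest half-step", which makes adjacent categories 0.5 apart. Code < 1.0 as 0.5 and > 3.0 as 3.5. There are 7 × 6 / 2 = 21 possible upward changes. Requiring a rise of at least 2.0 units gives 3 qualifying changes from < 1.0, 2 from 1.0 and 1 from 1.5, so 6 of 21. These are exactly the SAP's changes. A rule of two adjacent half-step categories would give 15 of 21 and does not match. So 2-step means two full grades, and the SAP's list is complete for this scale.

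**2. Ceiling.** Largest possible rise = 3.5 − baseline.

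| Baseline | Largest rise | Can qualify |
|---|---|---|
| < 1.0 | 3.0 | yes |
| 1.0 | 2.5 | yes |
| 1.5 | 2.0 | yes |
| 2.0 | 1.5 | no |
| 2.5 | 1.0 | no |
| 3.0 | 0.5 | no |
| > 3.0 | 0 | no |

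From 2.0 or higher there are 3 + 2 + 1 = 6 upward changes, and none qualifies. All six are visible in the per-type shift tables. A subject is unable to qualify only if all six components (2 eyes × 3 types) are at 2.0 or higher or ungradable.

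**3. Surgery.** Follow one eye and opacity type under the worst-grade rule:

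- Baseline < 1.0, graded 2.5, then removed: rise 2.5 − 0.5 = 2.0. Counted, because the grade before surgery is kept.
- Baseline 1.5, graded 2.5, then removed: rise 1.0. Not counted; the shift table shows 1.5 to 2.5.
- Baseline 2.0, still graded 2.0, then removed: rise 0. Not counted; the shift table shows 2.0 to 2.0, which is no change.

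Let s be the share of subjects with on-study cataract surgery who never meet the graded rule in any component. On a common denominator, (graded increase or surgery) − (graded increase) = s. The documents do not give s. As an assumption only, s = 2% to 10% of the protocol's estimated 400 subjects is 0.02 × 400 = 8 to 0.10 × 400 = 40 subjects.

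**4. Denominator.** Let q be the share of subjects with no component able to qualify, and r the rate among the rest. If everyone is kept in, the reported rate is r × (1 − q). The documents do not give q or r. Assuming r = 10%:

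| q | Reported |
|---|---|
| 2% | 9.8% |
| 5% | 9.5% |
| 10% | 9.0% |
| 20% | 8.0% |
| 30% | 7.0% |

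**5. Code 8.0.** If the largest value is taken literally, one ungradable visit ranks above 3.0. Any component at baseline 1.5 or lower would then become a 2-step increase. This error would run upward.

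**The case against.** The strongest reply is that the lens data are shown in several other ways.

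- Graded rises from 2.0, 2.5 and 3.0 appear in three shift tables.
- A subject with one dense component can still qualify through the other eye or another opacity type.
- A qualifying grade recorded before surgery still counts.
- Cataracts are among the uveitis-related events in the adverse event overview (SAP 11.1), which is also given per 100 subject-years, and worsening of an existing condition is reportable (Protocol 6.1.1.1).
- Exclusion criterion 2 keeps out lenses likely to need surgery during the trial.
- The table specifications are in a separate document (SAP 12.0) and may state a denominator.

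Most of this stands, and it rules out some stronger readings. A reader might infer that the worst lens outcomes in general are counted as no progression. The shift tables and the any-eye, any-type rule show otherwise, and the 2.0 limit is a property of a capped scale, not a forgotten line. A reader might also take the 20% extraction in non-implanted eyes reported in Protocol 3.4 as the size of the problem. That figure concerns eyes in a 3-year implant trial, not subjects here, and nothing says those operations came before a two-grade rise. Nor do the documents show that grading of a phakic fellow eye stops. The pseudophakia sentence refers to a subject, but Protocol 5.1 calls for both eyes to be evaluated and SAP 7.1 summarises AREDS grades by eye.

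The reply does not reach surgery before a qualifying grade. The shift tables use the same seven categories, so they miss it too. Adverse event counts depend on what investigators report, and standardised grading is there to provide a measure that does not.

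**Conclusion.** The point holds for surgery. Under SAP 11.6 as written, an eye operated on before a qualifying grade counts as having no 2-step increase, and its shift-table entry stays at its last grade before surgery. Scoring it as a non-event is the default reading of a section that is silent on surgery. This gap can only understate lens progression, by the share s in the working. That share cannot be estimated from the documents, and exclusion criterion 2 should keep it down.

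The ceiling at 2.0 is a lesser point. It calls for a stated at-risk denominator and is not evidence of hidden progression. The missing rule for code 8.0 could bias the variable the other way. The subject-or-eye wording is a clarification. Since the analysis is descriptive, with shift tables and adverse events alongside, this is a cheap improvement and not a threat to the trial's conclusions.

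**What to change.** In SAP 11.6:

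1. Keep the graded 2-step variable and report beside it a second one: 2-step increase, or cataract surgery/new pseudophakia after M11-327 baseline, in at least one eye. It is a different endpoint, so it should accompany the graded one, not replace it.
2. Add a cataract surgery/pseudophakia category to the post-baseline side of the three lens shift tables.
3. For the graded-only variable, use as denominator subjects with at least one phakic eye that has at least one opacity type graded 1.5 or less at baseline.
4. Treat code 8.0 as missing, never as the largest value.

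In Protocol 5.3.1.1, make the pseudophakia sentence refer to an eye instead of a subject, so that grading of a phakic fellow eye clearly continues.

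The cost is SAP wording and a small amount of programming. SAP 5.1 already requires subjects with on-study cataract surgery to be identified. If only subject-level surgery status is held, the operated eye must be collected. The cataract figure will look less favourable.

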Using the AREDS standard photographs as reference, the degree of lens opacity will be graded for each type: nuclear, cortical, and posterior subcapsular (PSC) (Table 3).^{37,38} See Appendix F for further instructions regarding lens opacity grading procedures.

Table 3. Lens Opacity Grading

Grading for Nuclear Lens Opacity	
< 1.0	no nuclear opacity, or less than NS Std. No. 1
1.0	opacity similar to NS No. 1
1.5	opacity between NS No. 1 and NS Std. No. 2
2.0	opacity similar to NS No. 2
2.5	opacity between NS No. 2 and NS Std. No. 3
3.0	opacity similar to NS No. 3
> 3.0	opacity greater than NS No. 3
8.0	cannot evaluate
Grading for Cortical Lens Opacity	
< 1.0	no cortical opacity, or opacity obviously less than CO Std. No. 1
1.0	opacity similar to cortical opacity Std. No. 1
1.5	opacity between CO Std. No. 1 and Std. No. 2
2.0	opacity similar to CO Std. No. 2
2.5	opacity between CO Std. No. 2 and Std. No. 3
3.0	opacity similar to CO No. 3
> 3.0	cortical opacity obviously greater than Std. No. 3
8.0	cannot evaluate
Grading for Posterior Subcapsular (PSC) Opacity	
< 1.0	no PSC opacity, or opacity obviously < PSC Std. No. 1
1.0	opacity similar to PSC No. 1
1.5	opacity between PSC No. 1 and Std. No. 2
2.0	opacity similar to PSC No. 2
2.5	opacity between PSC No. 2 and Std. No. 3
3.0	opacity similar to PSC No. 3
> 3.0	PSC obviously greater than PSC No. 3
8.0	cannot evaluate

Optical Coherence Tomography

Optical Coherence Tomography will be performed at every visit. Sites must use one of three OCT machines for this clinical trial to determine central retinal thickness and the presence of macular edema:

- Stratus OCT (Carl Zeiss Meditec, Inc.)
- Cirrus HD-OCT (Carl Zeiss Meditec, Inc.)
- Spectralis (Heidelberg Engineering)

Each subject will undergo OCT measurements of the central retinal thickness (1 mm subfield) to evaluate for macular edema at every visit using the same protocol approved machine throughout the study. The same OCT machine that was used in Study M10-877 or Study M10-880 should be used in Study M11-327. OCT images will be sent to the Central Reader for transmission to AbbVie. Although it is preferred to complete the OCT measurements following pupil dilation, it is important that the site conducts the scans consistently across each subject (using the same model of OCT device for each patient) throughout the study.

Tonometry

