Tonometry will be performed at every visit to measure the intraocular pressure for both eyes. Applanation tonometry is preferred but non-contact tonometry can also be used if the site does not have the equipment to perform applanation tonometry. However, the same technique should be used for all visits for an individual patient.

Dilated Indirect Ophthalmoscopy

Subject's eyes should be dilated in preparation for indirect ophthalmoscopy. The examination technique and instrument used should remain consistent for each subject throughout the study.

Dilated indirect ophthalmoscopy is performed to determine both vitreous haze grading and the absence/presence of inflammatory chorioretinal and/or inflammatory retinal vascular lesions.

Lesion location(s), number, size(s) and whether the lesions are active or inactive should be documented with a retinal drawing in the subject's source documentation, if a lesion is identified.

Grading of vitreous haze (Table 4) will be based on the publication from the National Eye Institute (NEI) which has also been adapted by the SUN working group.^{3,39}

Sites will use the standard photographs given to them by the sponsor and the description in Table 4 when determining the grade for vitreous haze.

Table 4. Vitreous Haze Grading

Grade	Description
0	No evident vitreal haze
0.5 +	Slight blurring of the optic disc margin because of the haze; normal striations and reflex of the nerve fiber layer cannot be visualized
1 +	Permits a better definition of both the optic nerve head and the retinal vessels (compared to higher grades)
2 +	Permits better visualization of the retinal vessels (compared to higher grades)
3 +	Permits the observer to see the optic nerve head, but the borders are quite blurry
4 +	Optic nerve head is obscured

At all visits dilated indirect ophthalmoscopy will be performed to determine the presence/absence of new inflammatory chorioretinal and/or inflammatory retinal vascular lesions compared to the findings from the final visit of the parent study (Study M10-877 or Study M10-880) based on the Investigators' clinical judgment.

Physical Examination

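### SAP 11.6 tabulates intraocular pressure only against its highest reading, so the shift table cannot show falls into its own 0–9 mmHg band unless every later reading is 9 or less

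*SAP*

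**What the plan says.** SAP 11.6 lists five other safety variables. The first is "Intraocular pressure (0–9, 10–21, 22–25, 26–30, > 30 mmHg"; the others are three lens opacity scales and a derived "2-step increase in lens opacity". One rule covers them all: a shift table of the baseline category "versus the worst observations (i.e., largest values) in these categories".

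The data come from the visit schedule in Protocol 5.3.1.1: "Tonometry will be performed at every visit to measure the intraocular pressure for both eyes". Hypotony is on the list of uveitis-related events in Protocol 6.1.1.1.1 and again in the adverse event overview of SAP 11.1.

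Elsewhere the SAP looks in both directions. For vital signs, section 11.5 summarises "Mean changes from baseline in Study M11-327 to the minimum value, maximum value, and final value in the vital signs variables". Section 11.2 does the same for quantitative laboratory parameters. For liver tests, section 11.4 builds shift tables of baseline "versus the min/max/final value in these 5 categories".

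On the lens, Protocol Table 3 has a code 8.0, "cannot evaluate", on each of the three scales. SAP 7.1 and 11.6 list seven grades per scale, for example "Posterior subcapsular opacity (grade < 1.0, 1.0, 1.5, 2.0, 2.5, 3.0, > 3.0" mmHg-free and without 8.0. Neither section says what is done with that code.

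**The concern.** Intraocular pressure can be harmful in either direction, and the plan recognises this: it names both raised pressure and hypotony as uveitis-related events and gives the table a low band. A rule that equates worst with largest suits lens opacity, where a higher grade is always worse. Carried over to pressure, it discards the low side.

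What is at stake is the measured evidence on low pressure. In the SAP, pressure appears in the baseline summary of section 7.1 and in the shift table of 11.6, and nowhere among the efficacy variables of section 10. If the shift table cannot show falls, the specified analyses show low pressure only when an investigator reports it as an adverse event, although both eyes are measured at every visit. Long-term safety is the study's primary objective.

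**Working it through.** The documents state no count, rate or precision on this point, so there is no figure to reproduce. The check applies the rule as written. I take worst to mean the largest post-baseline reading and work eye by eye; section 11.6 counts subjects and does not say how the two eyes are combined.

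**1. When the 0–9 column is reached.** For post-baseline readings x1, …, xn, the largest is at most 9 only if every xi is at most 9. One reading of 10 or more moves the eye out of the column.

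**2. Worked sequences, using the 11.6 bands.**

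| Baseline (mmHg) | Post-baseline readings | Shift to largest (as planned) | Shift to lowest |
|---|---|---|---|
| 15 | 4, 16 | 10–21 to 10–21 | 10–21 to 0–9 |
| 15 | 15, 14, 12, 5, 4, 6, 11, 13, 14 | 10–21 to 10–21 | 10–21 to 0–9 |
| within 0–9 | all within 0–9 except one of 12 | 0–9 to 10–21 | 0–9 to 0–9 |

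The second row has three consecutive low visits and still shows no change. In the third row the single recovered reading is the one labelled worst.

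**3. Illustration of how much is hidden.** Weeks 2, 4, 8, 12, 18, 30, 42, 54 and 66 give 9 scheduled post-baseline visits. Let p be the chance that a reading is 9 or less at a visit. The value of p is my assumption, and visits are treated as independent. The chance of at least one low reading is 1 − (1 − p)^9. The chance that the planned table shows 0–9 is p^9.

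| p | At least one low reading | Shown in the 0–9 column |
|---|---|---|
| 1% | 8.6% | 1 × 10⁻¹⁸ |
| 5% | 37.0% | 2 × 10⁻¹² |
| 10% | 61.3% | 1 × 10⁻⁹ |
| 20% | 86.6% | 5 × 10⁻⁷ |
| 50% | 99.8% | 0.2% |

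Real readings in one eye are correlated, so persistent low pressure would be shown more often than p^9 suggests. The table illustrates the direction of the loss and does not estimate it.

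**4. Lens code 8.0.** Take a baseline grade of 1.0 and later grades of 1.0 except one code of 8.0. With 8.0 treated as missing, the shift is 1.0 to 1.0 and there is no 2-step increase. With 8.0 processed as a number, the shift would be 1.0 to > 3.0 and the 2-step definition would be met, as it would from baselines of < 1.0 and 1.5. The two readings differ, and the SAP does not say in words which one applies.

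**The case against.** The best defence is that the table does what it says. Every shift it reports is a correct shift to the highest reading, and raised pressure is a concern the protocol states plainly: it names pressure elevation and glaucoma among the ocular effects of corticosteroids, has an exclusion criterion based on 25 mmHg or more, and lists increased pressure among the uveitis-related events. The 0–9 band also has a use, since it classifies baseline. Hypotony has its own place in the adverse event reporting, by investigators who have the tonometry results in front of them. Tables and listings are in a separate document (SAP 12.0), which might include individual low readings.

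Most of that stands. A reader might infer that the table gives wrong shifts, or that hypotony would go unreported; neither follows. What the defence does not answer is that no minimum-pressure analysis is specified, that adverse event reporting depends on judgement where measurements exist, and that calling a recovered reading the worst one is a mislabel.

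A reader might also infer that code 8.0 will be counted as the worst lens grade, fall in > 3.0, and inflate the 2-step increase and hence cataract progression. The documents do not support that. The SAP lists seven grades without 8.0 and restricts the rule to those categories, and Protocol Table 3 defines > 3.0 separately from the not-evaluable code. Excluding 8.0 is the natural reading, and under it the error is zero.

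**Conclusion.** The point holds for intraocular pressure. As specified, the shift table is one-sided: it cannot show a fall into 0–9 mmHg unless every post-baseline reading is 9 or less, and it labels recovery from low pressure as worst. This follows from the rule itself and needs no assumption about frequency, beyond reading worst as the largest post-baseline value. If the larger of the two eyes were used for each subject, the condition would be stricter still. The number of subjects affected is unknown.

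The consequence is moderate. The analysis is descriptive, the upward shifts are right and hypotony is captured as an adverse event. The change is still worth making, because it closes a gap in the primary, safety objective with data already in hand. The treatment of lens code 8.0 is a missing detail only, and nothing in the documents shows that it would be counted as worst.

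**What to change.** In SAP 11.6, give intraocular pressure its own rule: shift tables from baseline to the lowest and to the highest post-baseline value, in the existing five bands, labelled lowest and highest rather than worst. State whether they are produced per eye or per subject. The cost is one extra table and no new data.

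As a clarification, add one sentence that lens code 8.0 is not a grade and is set to missing before the worst grade and the 2-step increase are derived, with the number of not-evaluable gradings shown alongside.
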